6.3. Measures to Minimize Bias: Randomization and Blinding

All participants will be randomized, according to the randomization schedule generated prior to the study by the Biostatistics Department at GSK. Each participant will be dispensed blinded study intervention, labelled with his/her unique randomisation number, throughout the study. Each participant scheduled to receive study drug will receive a treatment allocation number when randomized. Participants will be randomized in a 3:1 ratio to receive study treatment (active drug: placebo) in this study.

This will be a double-blind study with participants and the site staff blinded. The site pharmacy will be unblinded.

The blind may be broken if, in the opinion of the Investigator, it is in the participant's best interest for the investigator to know the study treatment assignment. The Sponsor study team must be notified before the blind is broken unless identification of the study treatment is required for a medical emergency in which the knowledge of the specific blinded study treatment will affect the immediate management of the participant's condition. In this case, the Sponsor study team must be notified within 24 hours after breaking the blind. The date and reason that the blind was broken must be recorded in the source documentation and eCRF, as applicable.

Unblinded monitors, and in the event of a Quality Assurance audit, the auditor(s), will be allowed access to un-blinded study treatment records at the site to verify that randomization/dispensing has been done accurately.

A participant will be withdrawn from the study if that participant's intervention assignment is unblinded. The primary reason for the event or condition which led to the unblinding will be recorded in the CRF.

GSK's GCSP staff may unblind the intervention assignment for any participant with an SAE. If the SAE requires that an expedited regulatory report be sent to one or more regulatory agencies, a copy of the report, identifying the participant's intervention assignment, may be sent to investigators in accordance with local regulations and/or GSK policy.

6.4. Study Intervention Compliance

- When participants are dosed at the site, they will receive study intervention directly from the investigator or designee, under medical supervision. The date and time of each dose administered in the clinic will be recorded in the source documents. The dose of study intervention and study participant identification will be confirmed at the time of dosing by a member of the study site staff other than the person administering the study intervention.
- When participants self-administer study intervention at home (treatment period 3), compliance with study intervention will be assessed by direct questioning and counting returned **CCI** [REDACTED] during the site visits and documented in the source documents and relevant form. Deviation(s) from the prescribed dosage regimen should be recorded.
- A record of the quantity of GSK3923868 dispensed to and administered by each participant must be maintained and reconciled with study intervention and compliance records. Intervention start and stop dates, including dates for intervention delays and/or dose reductions will also be recorded.

6.5. Dose Modification

This protocol allows alteration from the currently outlined dosing schedule, but the maximum daily dose will not exceed 1500 mcg. Refer to Section [4.3](#) for dose justification.

The decision to proceed to the next dose level (either an increase or a decrease) will be made by the investigator and the study team on **an individual participant basis** and based on safety and tolerability data obtained in that participants at the prior dose level. The Investigator and Sponsor study team will review all available data for dose selection and/or modification. See Section [10.1.5](#) for more information.

6.5.1. Dose Escalation Stopping Criteria

6.5.1.1. Participant specific dose escalation stopping criteria

Participants who experience an exacerbation during the study will stop dose escalation and be withdrawn from the study. Refer to Section [7.1.4](#) for COPD exacerbation definition and stopping criteria.

In case of excessive use of rescue medication above 3-fold the participant's normal usage and in the absence of a precipitating cause such as Upper or Lower Respiratory Tract Infection, the participant will be urgently reviewed by the Investigator with a view to being withdrawn. The rescue medication usage will be specifically reviewed at next phone call and/or site visits.

6.5.1.2. Study specific dose escalation stopping criteria

Dose escalation and study will be temporarily halted and no further participants will be dosed until completion of a full safety review if one or more of the following criteria are met:

- One participant experiences a serious adverse event that is considered at least possibly related to the study drug.
- Two participants experience a severe adverse event or bronchospasm that is considered at least possibly related to the study drug.
- Two participants meet liver chemistry stopping criteria outlined in Section [7.1.1](#).
- Two participants meet QTc stopping criteria outlined in Section [7.1.2](#).
- Two participants meet spirometry stopping criteria outlined in Section [7.1.3](#).
- Two participants experience any severe non-serious adverse event considered clinically important by the Investigator and at least possibly related to the study drug.

Relevant reporting and discussion with the medical monitor, relevant GSK personnel, and the IRB/IEC will take place before resumption of dosing.

6.5.2. Pharmacokinetic Criteria for Dose Modification

There are no PK criteria for dose modification.

6.5.3. Retreatment Criteria

Retreatment is not permitted in this study.

6.6. Continued Access to Study Intervention after the End of the Study

Participants will not receive any additional treatment with GSK3923868 after completion of the study.

6.7. Treatment of Overdose

For this study, any dose of GSK3923868 inhalation powder greater than the planned nominal dose for the treatment period within a 24-hour time period up to minus 2 hour will be considered an overdose.

GSK does not recommend specific treatment for an overdose. The Investigator (or physician in charge of the participant at the time) will use clinical judgement to treat any overdose.

In the event of an overdose, the investigator/treating physician should:

1. Contact the medical monitor immediately.
2. Closely monitor the participant for AE/SAE and laboratory abnormalities for 24 hours.
3. Obtain a plasma sample for PK analysis if requested by the medical monitor (determined on a case-by-case basis).
4. Document the quantity of the excess dose as well as the duration of the overdosing in the CRF.

Decisions regarding dose interruptions or modifications will be made by the investigator in consultation with the Medical Monitor based on the clinical evaluation of the participant.

6.8. Concomitant Therapy

Any medication or vaccine (including over-the-counter or prescription medicines, recreational drugs, vitamins, and/or herbal supplements) or other specific categories of interest that the participant is receiving at the time of enrolment or receives during the study must be recorded along with:

- reason for use
- dates of administration including start and end dates
- dosage information including dose and frequency

The medical monitor should be contacted if there are any questions regarding concomitant or prior therapy.

Participants must abstain from taking prescription or non-prescription drugs (including recreational drugs, and dietary or herbal supplements) within 7 days (or 14 days if the drug is a potential enzyme inducer) or 5 half-lives (whichever is longer) before the start

of study intervention until completion of the follow-up visit, unless, in the opinion of the investigator and sponsor, the medication will not interfere with the study.

Participants are also permitted to use any medicines (e.g., beta-2 agonists, anticholinergics, methylxanthines, inhaled corticosteroids) to control their COPD. Other concomitant medications may be considered on a case-by-case basis by the investigator in consultation with the medical monitor if required.

Concomitant medication for concurrent well controlled medical conditions (e.g., hypertension, arthritis) may be continued, including opioids such as codeine.

Although GSK3923868 is not expected to be a perpetrator or victim of pharmacokinetic drug-drug interactions, strong CYP3A4 inhibitors (e.g., macrolides) are not permitted.

6.8.1. Rescue Medicine

Short-acting beta-2 agonists (e.g., salbutamol) or inhaled anticholinergic (e.g., ipratropium bromide) will be permitted to be used as rescue medication. This will be provided by the participant or, if necessary, supplied by the study site.

The use of rescue medications is allowable and at any time during the study. The date and time of rescue medication administration as well as the name and dosage regimen of the rescue medication must be recorded.

7. DISCONTINUATION OF STUDY INTERVENTION AND PARTICIPANT DISCONTINUATION/WITHDRAWAL

Study discontinuation specifics are detailed in [Appendix 1](#)

7.1. Discontinuation of Study Intervention

In rare instances, it may be necessary for a participant to permanently discontinue study intervention. If study intervention is permanently discontinued, the participant will then be withdrawn from the study. See the SOA for data to be collected at the time of discontinuation of study intervention and follow-up and for any further evaluations that need to be completed.

If the following criteria are met, the study will be temporarily paused, and all available safety data will be reviewed by the Sponsor and Investigator:

- One SAE occurring in 1 or more participants receiving GSK3923868 that is considered at least possibly related to the study drug

Further participants may be dosed only if, after review, the Sponsor and Investigator considers it safe to do so.

[figure not shown]
7.1.1. Liver Chemistry Stopping Criteria

Liver chemistry stopping, and increased monitoring criteria have been designed to assure participant safety and evaluate liver event etiology.

Discontinuation of study intervention for abnormal liver tests is required when:

- a participant meets one of the conditions outlined in [Figure 2](#) or
- in the presence of abnormal liver chemistry not meeting protocol-specified stopping rules, if the investigator believes that it is in the best interest of the participant.

Figure 2 Phase 1 Liver Chemistry Stopping Criteria – Liver Stopping Event Algorithm

Refer to [Section 10.6 \(Appendix 6\)](#) for liver safety actions and follow-up assessments. The investigator should consider that intensive muscular exercise can also cause asymptomatic elevations of liver function tests such as ALT and AST in using this algorithm [[Pettersson, 2007](#)].

7.1.2. QTc Stopping Criteria

The Fridericia QT correction (QTcF) formula will be used in the study.

A participant that meets either bulleted criteria based on the average of triplicate ECG readings will be considered for withdrawal from the study intervention:

- $QTcF > 500$ msec
- Change from baseline: $QTcF > 60$ msec

Baseline QTcF will be based on the pre-dose ECGs collected before the first dose.

If a clinically significant finding is identified after enrolment, the investigator or qualified designee will determine if the participant can continue in the study and if any change in participant management is needed. This review of the ECG printed at the time of collection must be documented. Any new clinically relevant finding should be reported as an AE.

Note: Single safety ECG assessments are performed following enrolment in this study. If a single ECG should meet the criteria above, obtain two further ECGs over a brief period (e.g., 5 to 10 minutes). The averaged QTcF value of the 3 ECGs should be used to determine whether the participant should be withdrawn from the study.

7.1.3. Spirometry Stopping Criteria

Any participant experiencing a reduction in FEV1 at the 1-hour post-dose compared to daily pre-dose value of > 20% will be withdrawn from the study.

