6. Dosing on Days 6 and 13 can be either at home or at the site. Day 14 dosing will be timed according to the Day 13 dosing time so that Day 14 pre-dose PK sample can be used as 24h post-dose in PK parameter calculations.
7. Patient diary card will be used to capture study intervention information, PEF measurements, AE/SAE and concomitant medication use. Dispense Day 1 (for evening entry), Day 2 to 5 (full day entry), and Day 6 (for morning entry) patient diary card before discharge on Day 1, and dispense Day 7 (for evening entry), Day 8 to 12 (full day entry), and Day 13 (for morning entry) patient diary card before discharge on Day 7, and dispense Day 14 (for evening entry) and Day 15 (morning entry) patient diary card before discharge on Day 14. The last diary card (dispensed on Day14) will be reviewed by the site via the phone call on Day 15, and returned to the site within 2 weeks from Day 15.
8. PEF measurements will be taken in triplicate twice each day (once in morning upon waking and once in the evening before bedtime) from Day 1 morning until Day 15 morning. PEF will be reviewed by the Investigator at each site visit or phone call (Day 15).
9. Includes systolic and diastolic blood pressure, heart rate, respiration rate and tympanic temperature. Tympanic temperature will be measured once per day in the morning only.
10. Clinical chemistry and hematology only.9

- The timing of planned study assessments may change during the course of the study based on emerging data/in-stream data review (e.g., to obtain data closer to the time of peak plasma concentrations) to ensure appropriate monitoring.
- Any changes in the timing of time points for any planned study assessments as the result of emerging pharmacokinetic/pharmacodynamic data from this study must be documented and approved by the relevant study team member and then archived in the sponsor and site study files but will not constitute a protocol amendment.

The Competent Authority (CA) and ethics committee (EC) will be informed of any safety issues that constitute a substantial amendment and require alteration of the safety monitoring scheme or amendment of the informed consent form (ICF). The changes will be approved by the CA and the EC before implementation.

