10.3.1. Definition of AE

AE Definition

 An AE is any untoward medical occurrence in a clinical study participant, temporally associated with the use of a study intervention, whether or not considered related to the study intervention. 
NOTE: An AE can therefore be any unfavorable and unintended sign (including an abnormal laboratory finding), symptom, or disease (new or exacerbated) temporally associated with the use of a study intervention.

Definition of Unsolicited and Solicited AE

 An unsolicited adverse event is an adverse event that was not solicited using a participant diary and that is communicated by a participant who has signed the informed consent. Unsolicited AEs include serious and non-serious AEs. Potential unsolicited AEs may be medically attended (i.e., symptoms or illnesses requiring a hospitalization, emergency room visit, or visit to/by a healthcare provider). The participants will be instructed to contact the site as soon as possible to report medically attended event(s), as well as any events that, though not medically attended, are of participant's concern. Detailed information about reported unsolicited AEs will be collected by qualified site personnel and documented in the participant's records. Unsolicited AEs that are not medically attended nor perceived as a concern by the participant will be collected during an interview with the participant and by review of available medical records at the next visit. Solicited AEs are predefined local and systemic events for which the participant is specifically questioned, and which are noted by the participant in their diary.

Events Meeting the AE Definition

 Any abnormal laboratory test results (hematology, clinical chemistry, or urinalysis) or other safety assessments (e.g., ECG, radiological scans, vital signs measurements), including those that worsen from baseline, considered clinically significant in the medical and scientific judgment of the investigator (i.e., not related to progression of underlying disease). Exacerbation of a chronic or intermittent pre-existing condition including either an increase in frequency and/or intensity of the condition. New condition detected or diagnosed after study intervention administration even though it may have been present before the start of the study.

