4.2.1. Definition of endpoints

Adverse events will be coded using the latest standard Medical Dictionary for Regulatory Affairs (MedDRA dictionary).

Grade 1 AEs are defined as mild. Grade 2 or higher AEs are defined as moderate or severe. This study will report AEs as mild, moderate, or severe.

CONFIDENTIAL

A study intervention-related AE/SAE is defined as an AE/SAE for which the investigator classifies the possible relationship to study intervention as “Yes”. A worst-case scenario approach will be taken to handle missing relatedness data, i.e., the summary table will include events with the relationship to study intervention as ‘Yes’ or missing.

Spirometry assessments are performed in triplicate with the highest value reported.

Whilst all data collected will be summarized, only measurements which are clinically significant at any timepoint between randomization and follow up will be reported as part of the primary endpoint.

Clinically significant values are defined as:

- Values in the potential clinical interest (PCI) ranges for laboratory values, vital signs, ECGs and spirometry.
- Values that achieve the study stopping criteria (protocol Section 7.1.3) for spirometry

The PCI ranges will be defined in the Section [6.2.1](#).

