4.2.2.2. Laboratory Data, Vital Signs, ECGs

For haematology, clinical chemistry, urinalysis, vital signs, ECG and spirometry data the following information will be summarised:

- 1) Clinically significant values at each visit
- 2) Raw and change from baseline values at each visit

Note: The first table is the only one included as part of the primary endpoint. Urinalysis data is only collected when there is an abnormal finding and so it is expected that urinalysis tables/listings will be sparse.

Laboratory Data

For laboratory data, separate tables for haematology, clinical chemistry and urinalysis tests will be produced. Laboratory evaluations including the analyses of Clinical chemistry tests, haematology tests and urinalysis, will be based on GSK Core Data Standards. Liver biochemical parameters will be included with clinical chemistry tests.

The details of the planned displays will be given in the OPS. Incidence of clinically significant laboratory parameters will be reported.

Vital Signs

The analyses of vital signs will be based on GSK Core Data Standards, unless otherwise specified.

In vital sign assessment, pulse rate, respiratory rate, tympanic temperature, and systolic and diastolic blood pressure will be assessed. Blood pressure and pulse measurement will be taken in the semi supine position.

Incidence of clinically significant vital sign parameters will be reported. Refer the normal ranges of laboratory parameters in the Section [6.2.1](#)

Further details of the planned displays will be given in OPS.

ECG

The QTc data analysis will use the collected values based on Fridericia formula.

The analysis of 12-lead ECG along with any ECG findings will be reported according to GSK Core Data Standards.

Safety ECGs will be performed in semi-supine position after at least 5 minutes rest. The parameters collected are PR, QRS, QT and QTc intervals.

Incidence of clinically significant ECG parameters will be reported. Refer the normal ranges of laboratory parameters in the Section [6.2.1](#)

Further details of the planned displays will be given in OPS.

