4.2.2.3. Lung Function Measurements

Spirometry

Spirometry data will include FEV1 measurements.

For spirometry data the following information will be summarised:

- 1) Clinically significant values at each visit
- 2) Raw and change from baseline values at each visit

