6.2. Appendix 2 Data Derivations Rule

6.2.1. Criteria for Potential Clinical Importance

- **Laboratory Values**

Haematology				
Laboratory Parameter	Units	Category	Clinical Concern Range	
			Low Flag (<x)	High Flag (>x)
Platelet Count	10 ⁹ /L		31	900
RBC Count	10 ¹² /L		4.2	5.9
Hemoglobin	g/L	Male	90	180
		Female	90	180
Hematocrit	fraction of 1			1.5*ULN
RBC Indices				
MCV	fL		0.75*LLN	1.5*ULN
MCH	pg		28	32
%Reticulocytes	%		na	2*ULN
WBC Count with differentials				
Lymphocytes	10 ⁹ /L		0.6	6
Neutrophil Count	10 ⁹ /L		1.5	12
Monocytes	10 ⁹ /L		na	2
Eosinophils	10 ⁹ /L		na	0.5
Basophils	10 ⁹ /L		na	2*ULN

CONFIDENTIAL

Clinical Chemistry				
Laboratory Parameter	Units	Category	Clinical Concern Range	
			Low Flag (<x)	High Flag (>x)
Albumin	g/L		32	50
Calcium	mmol/L		2.2	3.24
Creatinine	umol/L	Male 40-49 years	69	106
		Male 50-59 years	67.2	106
		Male 60-69 years	67.2	106
		Male 70+ years	59.2	106
		Female 40-49 years	52.2	106
		Female 50-59 years	53	106
		Female 60-69 years	53	106
		Female 70+ years	55.7	106
Glucose	mmol/L		4.0	7.8
BUN	mmol/L		2.5	15
Potassium	mmol/L		3.5	5.2
Sodium	mmol/L		136	145

CONFIDENTIAL

Liver Function			
Test Analyte	Units	Category	Clinical Concern Range
Alanine Aminotransferase (ALT) / Serum Glutamic-Pyruvic Transaminase (SGPT)	U/L	High	≥2x ULN
Aspartate Aminotransferase (AST) / Serum Glutamic-Oxaloacetic Transaminase (SGOT)	U/L	High	≥2x ULN
Alkaline phosphatase	U/L	High	≥2x ULN
T Bilirubin	μmol/L	High	≥ 1.5x ULN
Direct Bilirubin	μmol/L		0 – 6

- **ECG**

ECG Parameters	Unit	Clinical Concern range	
		Lower(<x)	Upper(>x)
Absolute			
Absolute QTc Interval	msec		> 600
Absolute PR Interval	msec	< 85	> 240
Absolute QRS Interval	msec	< 70	> 120
Change from Baseline			
Increase from Baseline QTc	msec		> 60

- **Vital Signs**

Vital Parameters (Absolute)	Unit	Clinical Concern range	
		Lower(<x)	Upper(>x)
Heart rate	bpm	35	110
Respiratory Rate	breaths/pm	8	20
Systolic blood pressure	mmHg	95	160
Diastolic Blood Pressure	mmHg	55	100
Temperature	°C	35.6	37.7

- **Spirometry**

Any participant experiencing a reduction in FEV1 at the 1-hour post-dose compared to daily pre-dose value of > 20%.

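### The only FEV1 limit compares the 1-hour value with the same day's pre-dose value, so loss built up during repeat dosing does not count towards it

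*Protocol*

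**What the plan says.** One FEV1 rule serves three purposes.

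- **Withdrawal (Protocol 7.1.3):** "Any participant experiencing a reduction in FEV1 at the 1-hour post-dose compared to daily pre-dose value of > 20% will be withdrawn".
- **Study halt (Protocol 6.5.1.2):** one trigger is "Two participants meet spirometry stopping criteria outlined in Section" 7.1.3.
- **Primary endpoint (SAP 4.2.1 and 6.2.1):** clinically significant spirometry means a value in the PCI range or one meeting 7.1.3. The only spirometry PCI in 6.2.1 is "Any participant experiencing a reduction in FEV1 at the 1-hour post-dose compared to daily pre-dose value of > 20" per cent. The two limbs are therefore the same rule.

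SAP 4.2.1 says that "only measurements which are clinically significant at any timepoint between randomization and follow up will be reported as part of the primary endpoint". For FEV1 the SAP also plans "Raw and change from baseline values at each visit" (4.2.2.3). Of the two displays, however, SAP 4.2.2.2, whose opening sentence covers spirometry, notes: "The first table is the only one included as part of the primary endpoint". That first table is the one of clinically significant values.

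The Period 3 schedule (Protocol 1.3.3) has FEV1 pre-dose and at 1 hour on Days 1, 7 and 14. The table columns are shifted in the text available here, and I read the last two marks as Day 14. Footnote 6 adds: "Dosing on Days 6 and 13 can be either at home or at the site".

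**The concern.** A same-day reference suits acute bronchospasm, the first risk listed in Protocol 2.3.1. It does not suit a gradual loss of lung function, which is how the second listed risk, respiratory tract irritancy, could show itself over 14 days. On Days 7 and 14 the pre-dose value is used only as that day's reference, so whatever has been lost by then is absorbed into it.

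This is the first use of the drug in COPD and the first outpatient study of it, and repeat dosing is part of the primary objective. Entry is allowed at a post-bronchodilator FEV1 of 40% predicted, so some participants will have little reserve. At stake is a primary spirometry table that could report no clinically significant values while a participant had lost a large part of their FEV1.

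The sponsor's QTc rule is built differently. Protocol 7.1.2 and the ECG part of SAP 6.2.1 both include a limit on change from baseline.

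**Working it through.** The plan gives no operating characteristics for the spirometry rule, so there is no planned figure to reproduce. The litre values and SDs below are assumptions; the documents give neither. The algebra in step 1 needs none of them.

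**1. What the rule measures.** Let P(d) be pre-dose FEV1 on day d and H(d) the 1-hour value. Write P(d) = P(1) × (1 − s), where s is the loss already present, and H(d) = P(d) × (1 − a), where a is the same-day drop.

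- Current rule: [P(d) − H(d)] / P(d) = a. The sustained loss s cancels.
- Against Period 3 Day 1 pre-dose: pre-dose fall = s; 1-hour fall = 1 − (1 − s)(1 − a).

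**2. Illustration.** Assumed pre-dose 1.50, 1.20 and 1.05 L, with a = 5% each day.

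| Day | Pre-dose (L) | 1 h (L) | Same-day drop | Pre-dose vs Day 1 | 1 h vs Day 1 pre-dose |
|---|---|---|---|---|---|
| 1 | 1.50 | 1.425 | 5% | – | −5.0% |
| 7 | 1.20 | 1.14 | 5% | −20.0% | −24.0% |
| 14 | 1.05 | 0.9975 | 5% | −30.0% | −33.5% |

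The current rule flags 0 of 3 days. A limit of more than 20% against Day 1 pre-dose flags 3 of the 4 values on Days 7 and 14; Day 7 pre-dose, at exactly 20.0%, is not flagged.

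**3. Range.** Sustained Day 14 falls of 25, 30, 40 and 50% with a = 0 all read 0% under the current rule. All four exceed 20% against Day 1 pre-dose by Day 14. If half the loss is present at Day 7, only the 50% case is flagged then (25%). Conversely, a 21% same-day drop with no sustained loss is flagged by both comparisons.

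**4. Exposure.** Home doses are Days 2–6 (5) plus Days 8–13 (6) = 11, or 9 if Days 6 and 13 are dosed on site, out of 14. All four FEV1 values on Days 7 and 14 follow this dosing, and neither 7.1.3 nor the PCI compares any of them with a value from before Period 3 dosing.

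**5. Weight of one participant.** With up to 9 on active in Period 3, one participant is 1/9 = 11 percentage points. A 30% relative fall from 40% predicted is 0.40 × 0.70 = 28% predicted. This is approximate, because entry FEV1 is post-bronchodilator and on-study values follow bronchodilator withholding.

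**6. Chance flags from an added limit.** Assume that the percentage difference between days is normal with SD 8–12% and no true change.

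- Per comparison: Φ(−20/8) = 0.0062; Φ(−20/12) = 0.0478.
- Proposed criterion, 12 participants × 4 values = 48: 0.30 to 2.29 expected flags.
- Pre-dose values only, 12 × 2 = 24: 0.15 to 1.15.

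Expected counts hold even though values within a participant are correlated.

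**7. Detection by an added limit.** For a true 30% fall at Day 14 pre-dose: Φ(10/12) = 0.80 to Φ(10/8) = 0.89. For a true fall of exactly 20%: 0.50.

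**8. If an added pre-dose limit counted towards the halt.** Per participant over two days, 1 − (1 − p)² = 0.012 to 0.093. The probability that at least 2 of 12 are flagged is 0.009 to 0.310, assuming independence and no confirmatory repeat.

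**The case against.** The case for leaving the plan alone has substance.

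- **Other safeguards act.** Protocol 7.1.4 requires withdrawal for an exacerbation, defined by worsening symptoms and falling lung function that call for a change in treatment. Protocol 6.5.1.1 requires urgent review when rescue use exceeds three times normal without a precipitating cause such as infection. PEF is measured twice daily and reviewed, and any action limit may lie in the Study Reference Manual, which is not available here. The investigator may withdraw anyone for safety (7.2).
- **The primary endpoint is not blind.** Under Protocol 10.3.1, adverse events cover abnormal safety assessments, "including those that worsen from baseline, considered clinically significant in the medical and scientific judgment of the investigator". Adverse events are themselves a primary endpoint.
- **The prior risk is low.** The rat findings were minimal or slight and absent in the dog inhaled and rat intravenous studies, and lung deposition cover is 10-fold. Twice this dose, with daily FEV1, gave no evidence of bronchospasm over 14 days in healthy participants and 7 days in asthma.
- **The proposed reference is not drug-free.** By Protocol Table 1, every sequence has had at least one active single dose before Period 3.

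All of this stands and limits the point. A reader might infer that a sustained fall can never meet the rule, however large. The documents do not support that: a fall that begins as a drop of more than 20% between pre-dose and 1 hour on a clinic day does meet it, and noise can too (about 0.01% to 4.5% over Days 7 and 14, at an assumed within-day SD of 5–10%). A reader might also infer that no rule would act on such a fall. Sections 7.1.4 and 6.5.1.1 show otherwise.

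What remains is narrower. None of these routes sets a numeric FEV1 limit, and none feeds the spirometry part of the primary endpoint.

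**Conclusion.** The point holds as a gap in the FEV1 criterion, not as an absence of safety monitoring. The withdrawal rule, the only spirometry PCI and the spirometry halt count are one same-day comparison. Loss already present at pre-dose on Day 7 or Day 14 contributes nothing to it, and without a same-day drop above 20% the primary spirometry table has no entry. That sits poorly with an endpoint meant to cover any timepoint and repeat dosing. The data would still be visible in the change-from-baseline summary.

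The cancellation follows from the rule's wording and needs no assumption. The illustration, the detection probabilities and the chance-flag counts rest on assumed FEV1 values and SDs, and the Day 14 timing rests on my reading of a shifted table. With a low prior risk and several other routes open, this is a cheap improvement worth making, not a fault that undermines the trial.

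**What to change.** **Main change (SAP 6.2.1).** Keep the within-day rule and add a second spirometry PCI, shown as its own row in the table of clinically significant values: *FEV1 more than 20% below the Period 3 Day 1 pre-dose value at Day 7 or Day 14, pre-dose or 1-hour.* State that this reference isolates the repeat-dose effect, that it follows at least one active single dose plus washout, and that it may differ from the study baseline in SAP 4.1.2.

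The cost is one row on measurements already scheduled, plus the 0.3 to 2.3 chance flags from step 6. One chance flag moves incidence by 11 points on active (1/9) or 33 on placebo (1/3), so the row should stay separate from the within-day one.

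**Optional change (Protocol 7.1.3).** If pre-dose FEV1 on Day 7 or Day 14 is more than 20% below Period 3 Day 1 pre-dose, repeat spirometry; if confirmed, the investigator documents a review before that day's dose. State that this is a review trigger and does not count towards the 6.5.1.2 halt, given the 1–31% chance-halt figure in step 8. A same-session repeat reduces measurement error but not true day-to-day variation. The trigger is mainly useful at Day 7, since at Day 14 only one dose remains; in the illustration it would not fire until Day 14. The cost is one sentence and an occasional repeat test.
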